## 2.4 Treatments (study treatment, rescue medication, concomitant therapies, compliance)

### 2.4.1 Study treatment / compliance

The duration of ofatumumab exposure in days for the open-label treatment phase, open-label extension period and overall will be summarized descriptively as a continuous variable using the SAF. The duration of ofatumumab exposure will be calculated within each phase/period and overall, as follows:

- (date of last dose of ofatumumab – date of first dose of ofatumumab) + 1

The date of the last dose of ofatumumab during the open-label treatment phase and the date of the first dose of ofatumumab during the open-label extension period will be determined as outlined in [Section 5.6](#).

Adherence to and persistence on ofatumumab therapy will be evaluated through drug accountability and/or possession diary as outlined in [Section 2.12](#).

## Study duration

Study duration in days will be calculated as follows:

- [(date of last contact/EOS – date of first dose of ofatumumab) + 1] for ofatumumab-treated participants
- [(date of last contact/EOS – date of Week 0 visit) + 1] for healthy control participants

## Open-label treatment phase duration

Open-label treatment phase duration in days will be calculated as follows:

- [(date of Month 18 interim analysis data cut-off – date of first dose of ofatumumab) + 1] for ofatumumab-treated participants
- [(date of Month 18 interim analysis data cut-off – date of Week 0 visit) + 1] for healthy control participants

For participants who do not complete the Month 18 visit, the date of last contact/EOS will be used.

Study duration and open-label treatment phase duration will be summarized descriptively as continuous variables by Cohort using the SAF or HCAS, as appropriate.

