**Table 2 Month 18 interim analysis data cut-off for different participant scenarios**

Participant scenario	Cut-off	Participant data included in Month 18 interim analysis (primary analysis)
Completed Month 18 visit	Date of Month 18 visit + 7 days (inclusive)	All available data up to the date of the Month 18 visit + 7 days (inclusive)*
Did not complete Month 18 visit		
Discontinued study prior to Month 18 visit	None	All available data
Did not discontinue study prior to Month 18 visit	Date of next scheduled visit after Month 18 (exclusive)	All available data up to the date of the next scheduled visit (including home visit) after Month 18 (exclusive).** If the next scheduled visit after Month 18 has not been completed, all available data is used.

\* Including data such as adverse events, medications, non-drug therapies/procedures, protocol deviations and relapses that started prior to or on the date of the Month 18 visit + 7 days.

\*\* Including data such as adverse events, medications, non-drug therapies/procedures, protocol deviations and relapses that started prior to the date of the next scheduled visit (including home visit) after Month 18.

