#### 5.6 Ofatumumab dose dates during open-label treatment phase and open-label extension period

The date of the last dose of ofatumumab during the open-label treatment phase and the date of the first dose of ofatumumab during the open-label extension period will be determined according to the following three participant scenarios.

1. Completed Month 18 visit and continued into open-label extension period
  - a. Last dose date of ofatumumab during open-label treatment phase is last dose date < Month 18 visit date
  - b. First dose date of ofatumumab during open-label extension period is first dose date  $\geq$  Month 18 visit date
2. Completed Month 18 visit and did not continue into open-label extension period
  - a. Last dose date of ofatumumab during open-label treatment phase is last dose date  $\leq$  Month 18 visit date
3. Did not complete Month 18 visit
  - a. Last dose date of ofatumumab during open-label treatment phase is last dose date  $\leq$  Month 18 interim analysis data cut-off date
  - b. First dose date of ofatumumab during open-label extension period is first dose date > Month 18 interim analysis data cut-off date

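### The treatment-phase duration rule in SAP Section 2.4.1 departs from the SAP's own phase boundary for participants who miss Month 18 but stay, and can make the phase longer than the study when the study ends at Month 18

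*SAP*

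**What the plan says.** SAP Section 2.4.1 defines two durations. Both start at the first dose (the Week 0 visit for healthy controls), both are end date minus start date plus 1, and both are summarised by Cohort.

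- **Study duration** ends at last contact/EOS.
- **Open-label treatment phase duration** ends at the Month 18 interim analysis data cut-off, with one override: "For participants who do not complete the Month 18 visit, the date of last contact/EOS will be used".

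The cut-off comes from SAP Section 2.1.1, Table 2. For participants who completed Month 18 it is "Date of Month 18 visit + 7 days (inclusive"). Participants without a Month 18 visit are split into two rows. Those who discontinued the study have no cut-off. Those still in the study have "Date of next scheduled visit after Month 18 (exclusive"), unless that next visit was not completed, in which case all their data are used.

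Two other places use this boundary. The definition of treatment phase and extension period in Section 2.1.1 runs the treatment phase from Study Day 1 through the cut-off and puts anything later in the extension. Section 5.6, scenario 3 (Month 18 not completed) divides doses at the same point: "First dose date of ofatumumab during open-label extension period is first dose date > Month 18 interim analysis data cut-off date".

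Protocol Section 9.3 places the EOS visit at Month 18 for participants who do not enter the extension.

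**The concern.** The override treats everyone without a Month 18 visit alike, although Table 2 separates leavers from stayers. Protocol Section 8 says that a missed visit should not lead automatically to discontinuation, so the second group can exist. For such a participant the extension is counted as treatment phase in the duration table, while doses and events after the cut-off are assigned to the extension.

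The second problem is a missing cap. Phase duration for a Month 18 completer runs to visit + 7 days, but study duration stops at last contact/EOS. If the study ends at the Month 18 visit, the phase can come out longer than the study that contains it.

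At stake are the reported mean and maximum of one descriptive variable, shown by Cohort alongside study duration, where a reader would see the mismatch.

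**Working it through.** The documents state no phase duration in days, so there is no figure to reproduce. The check applies the SAP's formula, end day − Day 1 + 1, at scheduled days.

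**Inputs**
- Month 18 = Day 540 and Month 30/EOS = Day 900 (SAP Table 3). These are consistent: 18 × 30 = 540 and 30 × 30 = 900.
- Month 21 = Day 630 (Protocol Table 8-1). Each of these visits has a window of ±3 days.
- Cut-offs from SAP Table 2. EOS at Month 18 for non-extenders, from Protocol Section 9.3.

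**Results by type of participant (days)**

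| Participant | Phase by Section 2.4.1 | Phase by Table 2 and the phase definition | Study duration |
|---|---|---|---|
| Misses Month 18, attends Month 21, EOS Day 900 | 900 | 630 − 1 = 629 | 900 |
| Completes Month 18, study ends there, no later contact | 540 + 7 = 547 | 547 | 540 |
| Completes Month 18, continues to Day 900 | 547 | 547 | 900 |
| Discontinues, last contact Day 300 (illustration) | 300 | no cut-off; last contact is the natural end | 300 |

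**First row.** The excess is 900 − 629 = 271 days, and 271/629 = 43%. With the visit windows, 897 to 903 days compares with 626 to 632.

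**Second row.** The phase exceeds the study by 7 days, and 7/540 = 1.3%. At the window limits it is 544 against 537 and 550 against 543.

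**Third and fourth rows.** No conflict.

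**Effect on the summary.** The documents do not give the number of participants in the first row, so 1, 3 and 5 are assumed. The cohort mean rises by k × 271/n:
- n = 118: 2.3, 6.9 and 11.5 days
- n = 50: 5.4, 16.3 and 27.1 days

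One such participant is enough to bring the maximum to about 900. For the second row, if a share p of a cohort is affected, the mean phase duration is up to 7 × p days too long, so never more than 7.

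**The case against.** The strongest reply is that the override has an obvious purpose. Table 2 gives discontinuers no cut-off, so the formula needs a substitute end date, and last contact/EOS is the right one. On that view only a qualifier is missing. I agree, but as written the sentence also covers participants for whom Table 2 does supply a date.

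Further points limit the reach, and they stand:

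- Protocol Table 8-1 schedules consent for the extension at Month 18, so participants who miss that visit yet continue should be few.
- At the Month 18 analysis, Table 2 restricts the data. If last contact is taken from the cut data, the example gives at most about 629 days. The SAP does not say whether that date is truncated. The full 900 belongs to the final analysis, which takes data through Month 30, or to an untruncated date.
- If the next scheduled visit was not completed, Table 2 uses all available data and the override contradicts nothing.
- The corrected value in the example is 629 days, not 540. The correction restores agreement with the SAP's phase definition; it does not produce exactly 18 months.
- The 7-day excess requires that nothing is recorded after the Month 18 visit. An MRI is allowed within 7 days either side of the visit, so a later contact can shrink or remove the excess. The case is plainest for healthy controls, who have no safety follow-up.

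A reader might also infer that every Month 18 completer's phase is 7 days too long and should end at the visit itself. The documents do not support this. Table 2 and the phase definition make visit + 7 days part of the treatment phase, so 547 is correct for completers who continue. Only the dose split in Section 5.6, scenario 1 uses the visit date. Ending the phase at the visit would leave adverse events on Days 541 to 547 in a phase whose reported duration had already closed.

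**Conclusion.** The point holds in two limited parts.

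1. For a participant who misses Month 18, stays in the study and has a later scheduled visit, the Section 2.4.1 override contradicts Table 2, the phase definition and Section 5.6, scenario 3. The result is up to 900 days instead of 629. The 900 is an upper end that assumes follow-up to Month 30 and an untruncated last-contact date.
2. For a participant whose study ends at the Month 18 visit with no later recorded contact, the uncapped cut-off gives a phase up to 7 days longer than the study.

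This takes Table 2 as governing the cut-off, because the phase definition refers to it; SAP Section 2.13 still describes the data as running to the Month 18 visit date.

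The consequence is small. Phase duration is descriptive. It does not enter NEDA-3, drug exposure (calculated from dose dates), the annualised relapse and T2 lesion rates (days in Months 6 to 18) or the adverse event tables (counts and percentages). How many participants are affected cannot be determined from the documents.

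**What to change.** In SAP Section 2.4.1, replace the override with two rules for both cohorts:

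- Participants who discontinued the study before Month 18: the phase ends at last contact/EOS.
- All other participants: the phase ends at the earlier of the Table 2 cut-off date and last contact/EOS. Where Table 2 supplies no date because the next scheduled visit was not completed, use last contact/EOS.

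In the worked cases this gives 629 days for the participant who misses Month 18 and stays, and 540 for both durations when the study ends at Month 18. The 547 days for completers who continue and the value for discontinuers do not change. The phase can then never exceed the study.

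The cost is a short wording change and one derivation. No new data are needed, and no other planned analysis changes.

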### 2.4.1.1 Visit windows

Visit windows will be used for data that are summarized by visit; they are based on the study evaluation schedule and comprise a set of days around the nominal visit day. When visit windows are used, all visits, including unscheduled visits, will be re-aligned (i.e., they will be mapped into one of the visit windows). In the case of major deviations from the visit schedule, or due to unscheduled visits, several assessments for a participant may fall in a particular visit window (either scheduled or unscheduled). Approaches for handling multiple assessments in a visit window are outlined below.

The following steps are used to determine the cut-offs for post-baseline visit windows:

- The visit window associated with the previous assessment ends prior to the middle point; the visit window associated with the latter assessment begins after the middle point. In case the middle point is an exact study day, it will belong to the previous assessment.
- The visit window of the first post-baseline assessment starts with Study Day 2, unless otherwise indicated.

Tables 3, 4, 5 and 6 provide visit windows for applicable parameters.

**Table 3 Visit windows for EDSS / Kurtzke Functional Systems Scores and Ambulation / NeuroQOLTM / PDDS / [REDACTED]**

Analysis visit	Nominal time point	Scheduled visit day (target Visit window (study days) study day)	
Baseline/Week 0	BSL/Wk0	1	≤1
Week 1	Wk1	7	2 to 10
Week 2	Wk2	14	11 to 21
Week 4	Wk4	28	22 to 59
Month 3	M3	90	60 to 135
Month 6	M6	180	136 to 270
Month 12	M12	360	271 to 450
Month 18	M18	540	451 to cut-off day
Month 30	M30/EOS	900	≥cut-off day + 1

Note:

- Baseline is derived as outlined in [Section 2.1.1](#).
- Cut-off day is the study day of the Month 18 interim analysis data cut-off described in [Section 2.1.1](#).

**Table 4 Visit windows for vital signs**

Analysis visit	Nominal time point	Scheduled visit day (target Visit window (study days) study day)	
Baseline/Week 0	BSL/Wk0	1	≤1
60 Minutes Post-Injection*	60 Minutes Post-Injection	1	1 (post-injection)
Week 1	Wk1	7	2 to 10
Week 2	Wk2	14	11 to 21
Week 4	Wk4	28	22 to 59
Month 3	M3	90	60 to 135
Month 6	M6	180	136 to 270
Month 12	M12	360	271 to 450
Month 18	M18	540	451 to cut-off day
Month 30	M30/EOS	900	≥cut-off day + 1

\* Only applicable to ofatumumab-treated participants.

Note:

- Baseline is derived as outlined in [Section 2.1.1](#).
- Cut-off day is the study day of the Month 18 interim analysis data cut-off described in [Section 2.1.1](#).

**Table 5** Visit windows for [REDACTED] /  
hematology and chemistry labs / smoking status

Analysis visit	Nominal time point	Scheduled visit day (target study day)	Visit window (study days)
Baseline/Week 0	BSL/Wk0	1	≤1
Month 18	M18	540	2 to cut-off day
Month 30	M30/EOS	900	≥cut-off day + 1

Note:

- Baseline is derived as outlined in [Section 2.1.1](#).
- Cut-off day is the study day of the Month 18 interim analysis data cut-off described in [Section 2.1.1](#)

**Table 6** Visit windows for MRI

Analysis visit	Nominal time point	Scheduled visit day (target study day)	Visit window (study days)
Baseline/Week 0	BSL/Wk0	1	≤1
Month 6	M6	180	2 to 270
Month 12	M12	360	271 to 450
Month 18	M18	540	451 to cut-off day
Month 30	M30/EOS	900	≥cut-off day + 1

Note:

- Baseline is derived as outlined in [Section 2.1.1](#).
- Cut-off day is the study day of the Month 18 interim analysis data cut-off described in [Section 2.1.1](#).

## Multiple assessments

When there are multiple assessments in a particular visit window, the rules outlined below are applied to select one value “representing” the participant in summary statistics for that visit window. All assessments will be displayed in listings.

- **Baseline:** The last non-missing assessment, including unscheduled assessments, obtained prior to or on the date of the first dose of ofatumumab for ofatumumab-treated participants (Study Day 1), or prior to or on the date of the Week 0 visit for healthy control participants (Study Day 1). If there are multiple assessments on Study Day 1, the following rules apply:
  - a. If a complete assessment time exists:
    - The latest assessment prior to the time of the first dose of ofatumumab will be used for ofatumumab-treated participants.
    - If there is no assessment prior to the time of the first dose of ofatumumab, the earliest assessment post time of first dose of ofatumumab will be used for ofatumumab-treated participants.
- **Post-baseline:** For post-baseline visit windows, the following rules apply (unless otherwise specified):
  - a. For *continuous variables*, the assessment with the study day that is closest to the target study day is selected. If two assessments are equidistant from the target study day, the earlier assessment is selected (if one of the two equidistant assessments is an unscheduled assessment, it should be excluded from consideration).
  - b. For *categorical variables*, the assessment with the worst result is selected.

If categorical variables are based on continuous variables, the analysis visit will be assigned to the continuous variable, and this analysis visit will be used for the derived categorical variable.

In situations where the same assessment is performed more than once on the same date, the following applies:

- a. If a complete assessment time exists, the earliest assessment will be used.

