O = Ofatumumab participant

H = Healthy Control

X = assessment to be recorded in the clinical database or received electronically from a vendor

S = assessment to be recorded in the source documentation only

■ [Redacted]

² Relapse assessment will be performed in scheduled, as well as unscheduled visits as deemed necessary by the Investigator or designee. Assessment can be done on site or via remote procedures

³ Urine β-hCG will be conducted monthly, at home, as well as, at defined clinical visits (scheduled and unscheduled)

[Redacted]

⁴ Assessment during an unscheduled visit will be performed as deemed necessary by the investigator, **except** for vital signs and evaluation of AE, which are mandatory at each visit

⁶ Participants are not required to come to the study site. Remote contact with participants, by site staff around the time of at-home, self-administration of ofatumumab should query about any new or worsening symptoms warranting an unscheduled visit, MS relapse, compliance with study treatment [REDACTED], adverse events, and compliance with contraception requirements (when applicable). The method of contact can be via telephone, email, video conference or text message depending on the preference of each participant

⁷ For the first injection, vital signs should be obtained 30-60 minutes before sc injection and again approximately 60 minutes post-injection

⁸ All lab assessments should be taken prior to dosing at the Day 1 visit. For any later biomarker visits, if the visit coincides with the day the monthly injection is scheduled, the subject should not take the injection in the morning before coming to the site so that the biomarker sample can be drawn before the injection

⁹ Labs must be drawn to allow adequate time for results to be obtained before first study drug administration to ensure participant's eligibility

¹⁰ Urine dipstick: If abnormal send full urinalysis to central laboratory

¹² Data for safety follow-up visit will be captured in source documentation only. Safety follow-up participants are not required to come to study site and lab assessments should be done locally

¹³ Only for participants continuing onto the 12-month open-label extension period

¹⁴ Gadolinium will not be given to healthy controls and gadolinium enhanced T1 MRI imaging will not be conducted in healthy controls

¹⁵ The C-SSRS must be administered at either screening or baseline, then at every on-site visit thereafter until End of Study (EOS)

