Vital signs	
Vital signs will include the collection of sitting pulse rate, sitting systolic and diastolic blood pressure, and body temperature (oral, or per local practice; recorded in °C).
 
After the subject has been sitting for 5 minutes, with back supported and both feet placed on the floor, systolic and diastolic blood pressure will be measured using an automated validated device, with an appropriately sized cuff. In case the cuff sizes available are not large enough for the participant's arm circumference, a sphygmomanometer with an appropriately sized cuff may be used.
 
For the first injection, vital signs should be obtained 30-60 minutes before sc injection and again approximately 60 minutes post-injection. If premedication is administered, the vital signs should be taken prior to pre-medication administration.

Height and weight	
Height in centimeters (cm) and body weight (to the nearest 0.1 kilogram (kg) in indoor clothing, but without shoes) will be measured as specified in Table 8-1.

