## Baseline

Unless otherwise specified, baseline will be derived as follows:

- For ofatumumab-treated participants, baseline is the last non-missing assessment, including unscheduled assessments, obtained prior to or on the date of the first dose of ofatumumab.
- For healthy control participants, baseline is the last non-missing assessment, including unscheduled assessments, obtained prior to or on the date of the Week 0 visit.

Unless otherwise specified, all assessments obtained after the date of the first dose of ofatumumab for ofatumumab-treated participants, or after the date of the Week 0 visit for healthy control participants, are considered post-baseline assessments.

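### The SAP's date-based baseline rule can make the Day 1 post-injection vital-sign reading the baseline when no usable pre-injection Day 1 reading exists, although a screening reading is scheduled

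*SAP*

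**What the plan says.** - **General rule (SAP 2.1.1, Baseline).** For ofatumumab participants, "baseline is the last non-missing assessment, including unscheduled assessments, obtained prior to or on the date of the first dose of ofatumumab". The mirror definition is also by date: the post-baseline class is "all assessments obtained after the date of the first dose of ofatumumab". A reading taken on Day 1 after the injection is therefore not classed as post-baseline.
- **Day 1 tie-break (SAP 2.4.1.1, Multiple assessments).** The date rule is repeated, followed by "If there are multiple assessments on Study Day 1, the following rules apply". One branch is then given, opening "If a complete assessment time exists". It prefers the last reading timed before the injection. Failing that, "the earliest assessment post time of first dose of ofatumumab will be used for ofatumumab-treated participants". There is no branch for missing times and no instruction to go back to Screening.
- **Scheduled readings (Protocol Table 8-3 and Table 8-1 footnote 7).** For the first injection, "vital signs should be obtained 30-60 minutes before sc injection and again approximately 60 minutes post-injection". Table 8-1 also schedules vital signs at Screening.
- **Windows (SAP Table 4).** Baseline/Week 0 covers study days up to and including 1. The 60-minute reading has a separate row, on Day 1 after injection. The table note refers back to SAP 2.1.1 for how baseline is derived.
- **Use (SAP 2.7.4.1).** Vital-sign values and changes from baseline are summarized descriptively by time point.

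**The concern.** A baseline is meant to be an untreated value. Here the written rule can select a treated value while an untreated one is on file. The 60-minute time point suffers most, because the same number would serve as both baseline and follow-up.

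That time point has some interest. Protocol 4.5 cites systemic injection-related reactions in 20.6% of ofatumumab patients in the Phase 3 studies (15.3% on teriflunomide) and ties them to the first injection. SAP 2.7.1.1 summarizes systemic injection reactions as an event category. The Day 1 change in blood pressure, pulse and temperature is the natural numerical companion to that summary, although neither document states this as its purpose. For an affected participant the table would show no acute change whatever happened.

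**Working it through.** The plan states no figure on this point, so there is none to reproduce. The check applies the rule as written to the possible Day 1 records.

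**Order of the rule.** (1) Keep readings dated on or before the first dose. (2) Take the last of these, so a Day 1 reading outranks Screening whether it was taken before or after the injection. (3) If there are two or more Day 1 readings with complete times, take the last pre-injection one, or failing that the first post-injection one.

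**Illustrative systolic values (assumed, not from the documents).** Screening 118, pre-injection 120, 60 minutes post-injection 128, and in one case a further reading of 126 at 90 minutes. The change formula in SAP 2.1.1 is follow-up minus baseline, so the 60-minute change is 128 − baseline.

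| Day 1 readings | What decides | Baseline as written | 60-minute change | Baseline with the fix | Change with the fix |
|---|---|---|---|---|---|
| Timed pre and post | Timed branch | 120 | 128 − 120 = +8 | 120 | +8 |
| Post only | Date rule | 128 | 128 − 128 = 0 | 118 | 128 − 118 = +10 |
| Two timed post, no pre | Timed branch | 128 | 0 | 118 | +10 |
| Untimed pre, timed post | Timed branch, if only a timed reading can count as pre-dose | 128 | 0 | 120 by label | +8 |
| Both untimed | No branch applies | Undefined | Undefined | 120 by label | +8 |

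In the last two rows, if no pre-/post-injection label exists either, the fix uses Screening: baseline 118, change +10.

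Three things follow.

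1. The sentence quoted from SAP 2.4.1.1 acts only with two or more Day 1 readings. A lone post-injection reading never reaches it; the date rule selects that reading directly. Both texts therefore need the change.
2. The zero is confined to the 60-minute time point. At a later visit with value X, the post-only participant has change X − 128 instead of X − 118. That is a shift of −10, not a zero.
3. Screening (118) was available in every case and was never selected as the rule is written.

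**Size.** If a share f of participants has the 60-minute change set to zero, and these participants would otherwise have had the average change, the mean becomes (1 − f) times its true value. The shares below are assumptions, and all 118 are taken to have a 60-minute reading.

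- f = 2%: 0.02 × 118 = 2.4 participants; a mean of +8 becomes 0.98 × 8 = 7.84.
- f = 5%: 0.05 × 118 = 5.9 participants; 0.95 × 8 = 7.6.
- f = 10%: 0.10 × 118 = 11.8 participants; 0.90 × 8 = 7.2.

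**The case against.** The best defence is Table 4. It gives the 60-minute reading its own window, SAP 2.4.1.1 maps each visit into one window, and the tie-break chooses among readings within a window. On that reading the 60-minute value never competes for baseline, and Screening is what remains. The general definition also allows for exceptions specified elsewhere. This is a fair reading, and it is why the conclusion says *can* rather than *will*. It does not settle the matter: the Baseline window includes all of Day 1, the table's note sends the programmer back to the date rule, and no sentence excludes the reading.

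One could also count Screening as an assessment before the time of first dose. But the branch operates only among several Day 1 assessments, and the date rule has by then already passed over Screening.

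Other parts of the defence stand. The protocol asks for a pre-injection set, so failures should be rare. All assessments appear in listings, and injection reactions are summarized separately as adverse events.

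A reader might also infer that laboratory and urine baselines are affected. The visible documents do not support that. Table 8-1 footnote 8 says "All lab assessments should be taken prior to dosing at the Day 1 visit". Coagulation is kept in source documents only, no visible summary uses dipstick results, and hematology and chemistry are scheduled at Screening but not at the Baseline visit.

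**Conclusion.** The point holds for vital signs in ofatumumab participants. As written, the SAP can take a post-injection reading as baseline in preference to a scheduled screening reading. The 60-minute change is then zero, and later changes start from a post-dose value.

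The reach is small. The number affected cannot be derived from the documents, and the 2% to 10% range is only for scale. Proportional attenuation rests on the further assumption that affected participants are average. The summaries are descriptive, no hypothesis is tested, and NEDA-3 does not use these data.

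Two stronger readings should not be drawn. The first is that every participant without a timed pre-injection reading receives the 60-minute value as baseline. With wholly untimed readings the SAP is silent, so the result is undefined. The second is that the rule hides acute effects throughout the vital-sign tables. Participants with a timed pre-injection reading are unaffected, and later time points are shifted for the few affected participants, not zeroed.

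**What to change.** Amend SAP 2.1.1 (Baseline) and SAP 2.4.1.1 (Multiple assessments, Baseline) together, for vital signs only:

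- A reading in the Table 4 post-injection window, or otherwise taken after the first injection, cannot serve as baseline.
- Baseline is the last non-missing value before the injection, including Screening and unscheduled readings.
- Where Day 1 times are missing, classify readings by their nominal pre- or post-injection label.
- If no pre-injection value can be identified, baseline is missing.

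Leave the rule unchanged for patient-reported outcomes and other measures. Table 8-1 does not collect the patient-reported outcomes at Screening, so a general ban on same-day post-dose values could cost baselines there for no clear gain.

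The cost is a short addition in two places. Almost no vital-sign baselines should be lost, because a screening reading is scheduled. The drawback is that a screening baseline may be up to about 4 weeks old, so for the few affected participants the 60-minute change would include between-day variation. A footnote giving the number of participants with a screening baseline would make that visible.
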